Primary objective: To evaluate the feasibility (study design, methods, processes) and acceptability (family/child/clinician satisfaction, perceived usefulness) of conducting a RCT of a novel, brief, coaching intervention (SFC-Peds) for improving and sustaining PA and dietary habits in CWPD.

Secondary objective: To determine the responsiveness of selected outcome measures to SFC-Peds coaching over 12 months.

Principal research question: *“Is an efficacy trial to evaluate a six month SFC-Peds intervention to improve PA and dietary habits feasible to implement and acceptable to CWPD and families?”*

APPROACHES AND METHODS

Design: We will use a pilot RCT design [82] with two groups: One group (n=15) will work with a coach trained in SFC-Peds eight times over six months. The other group, the control group (n=15), will receive only standard printed materials at the start of the study. These materials will also be available to the SFC-Peds group to control for bias on study measures. The control group will allow us to control for information, maturation, repeated testing and attrition over the 12 month study [83]. All participants will receive standard care from existing clinicians who will not be delivering the SFC-Peds study intervention. The *feasibility* of trial processes, management, and resources will be assessed quantitatively. The *acceptability* of trial participation and coaching processes will be explored qualitatively. Qualitative enquiry lends insight into potential mechanisms of change and barriers to implementation and is therefore highly recommended when evaluating complex interventions [34].

Sample: Thirty children aged 10–18 inclusive and their parents who live within approximately two hours of Holland Bloorview Kids Rehabilitation Hospital (Toronto, ON) up to Thames Valley Children’s Centre (TVCC) (London, ON) will participate. The sites serve diverse socio-cultural communities.

Children and Teens in Charge of their Health: A feasibility study of solution-focused coaching to foster healthy lifestyles in children and young people with physical disabilities.

Child inclusion criteria:

- i) Between the age of 10 – 18 years inclusive
- ii) Diagnosis of SB or CP
- iii) Has physical capability to execute independent body movement with or without device
- iv) Cognitively able and willing to set PA or dietary goals
- v) Can communicate in English and respond to questions requiring some reflection and insight
- vi) Home internet connection

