- vii) Lives within 2 hours driving distance from Toronto up to London, Ontario OR willing to travel to either HB or TVCC for first in-person coaching session if randomized into coaching group

Child exclusion criteria:

- i) Surgery in past 6 months or upcoming 12 months that may impact PA or dietary intake (e.g. orthopedic surgery or neurosurgery)
- ii) Medical condition severely restricting diet
- iii) Underweight (less than fifth percentile)
- iv) Receiving specialist dietetic services

Parent inclusion criteria:

- i) Primary caregiver to a study participant
- viii) Can communicate in English and respond to questions requiring some reflection and insight

Sample size

Feasibility studies do not assess intervention efficacy and therefore do not require formal sample size calculations [33, 85]. The sample size ($n=30$) was set as a minimum needed to assess the key feasibility issues, as per feasibility best practices [86]. Fifteen SFC-Peds participants will suffice to show

Children and Teens in Charge of their Health: A feasibility study of solution-focused coaching to foster healthy lifestyles in children and young people with physical disabilities.

a tendency ($p < 0.10$) within the intervention group of behavioural change assessed by Goal Attainment Scaling (GAS; see ‘Outcomes’), equal to an effect size of 0.55 with a power of 0.80. The responsiveness of the secondary outcome measures will be compared with goal scores for evidence of concordance, e.g. a tendency of correlation between behavioural change and the Arc’s Self-Determination Scale. *Post hoc* estimates of variance will be key for the full trial’s design as they will inform the power calculations of the eventual RCT [85]. The sample size will allow us to assess recruitment success and show whether testing procedures, coaching goals and follow-up sessions are consistent across groups, mobility levels and sites. This sample size will also provide sufficient data for the qualitative work we are proposing to explore acceptability [87, 88].

Recruitment

We will recruit 15 children with SB and 15 children with CP (a total of 30 participants) and their parents from Holland Bloorview and TVCC.

Recruitment at Holland Bloorview

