At this session, the RC will clarify any concerns, and answer any questions clients or parents might have and will judge the child's capacity to provide informed consent, guided by a structured tool (see Appendix 3). If the RC judges the child to have answered questions about the study with reasonable understanding, the child will sign the Informed Consent Form (ICF) (see Appendix 4). Otherwise, a parent will sign the ICF and the child will provide their assent (see Appendix 5). For parents who are willing to participate in the interviews and parent measures the parent will sign the ICF for their own participation in the study. The RC obtaining informed assent from prospective participants (children) will familiarize the potential participant about assent by explaining what free, informed consent is and how research is different from clinical care. The RC will have an open and age appropriate discussion with each child to assess readiness for assent. The RC may consult the parent to identify accommodations to assist in decisions to participate. The assent and consent forms will be provided prior to this discussion in order for families to review them on their own. While meeting with the client and parent, the RC will clarify any concerns, and answer any questions clients or parents might have. During this process, the highly experienced RC will observe and listen for any verbal and nonverbal indications of dissent. Furthermore, the RC will ensure ongoing informed assent by reconfirming agreement to participate throughout the study. At the end of the study, the family will receive a study summary letter at the end of the study. The local REB fully endorses these processes.

Randomization

Once participants have provided written informed consent and completed all baseline measures, they will be randomized into the study. The PLAN procedure of SAS/STAT software will create a random sequence to test randomization. Randomization block size will not be known to research staff to ensure blinding. Group allocation occurs after baseline assessment, stratified by diagnosis and recruitment site.

Children and Teens in Charge of their Health: A feasibility study of solution-focused coaching to foster healthy lifestyles in children and young people with physical disabilities.

Standard care

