Intervention Measure of Engagement – Service Provider (PRIME-SP) (see Appendix 11) and will be assessed by the coaches after each coaching session [126].

STUDY OUTCOMES AND PROCEDURES

Study Procedures

After enrollment into the study, participants will complete the following assessments at the time points outlined below (see Appendix 12 for assessment schedule). Children in the SFC-Peds group will receive the eight 60 minute coaching sessions between Time 1 and Time 2.

Assessment Timings

To assess participant retention, the feasibility study will use four assessment points over 12 months as in the planned efficacy trial: **Time 1 Baseline** (immediately preceding randomization); **Time 2** (immediately post-intervention or 6 months post-baseline for control group +/- 2 weeks); **Time 3** (three months post-intervention or 9 months post-baseline for control group +/- 2 weeks); **Time 4** (6 months post-intervention or 12 months post-baseline for control group +/-4 weeks).

Study Assessments

PRIMARY OBJECTIVE: *To evaluate the feasibility and acceptability of conducting a RCT of a novel, brief, coaching intervention (SFC-Peds) for improving and sustaining PA and dietary habits in CWPD.*

Trial feasibility will be assessed using the following pre-identified criteria (as recommended [82]):

Recruitment	2–3 participants/month recruited over 12 months (for target sample size $n=30$)	$\geq 10\%$ recruitment response rate achieved (min. feasible RCT response rate [99])
Attrition	85% participants successfully complete study (i.e. complete T1 & T4 evaluations)	75% participants complete all assessments (i.e. protocol adherence)
Adherence	Successful completers participate in $\geq 75\%$	75% of the participants complete

Children and Teens in Charge of their Health: A feasibility study of solution-focused coaching to foster healthy lifestyles in children and young people with physical disabilities.

	meetings with coach	evaluations in ≤ 2 hrs (to assess burden)
Stratification	Intervention/control groups similar for age and gender	Intervention/control groups comparable on diagnosis and functional mobility
Fidelity	High intervention fidelity (>8/10 on the Solution-Focused Fidelity Instrument [98])	Challenges/ease of remote coaching (coach, child, family report)

Trial acceptability will be explored qualitatively:

Semi-Structured Survey

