Skinfold thickness: Skinfold thickness (SFT) is strongly associated with cardiovascular risk factors in children [136]. Tricep and subscapular skinfold thickness will be assessed, as per best practice [137] using Lange callipers (Cambridge Scientific Industries). Subscapular SFT in particular has

Children and Teens in Charge of their Health: A feasibility study of solution-focused coaching to foster healthy lifestyles in children and young people with physical disabilities.

previously demonstrated excellent test-retest reliability when conducted by skilled practitioners [127, 133]. The Slaughter equation will be used to assess body fat [138].

HOME AND ENVIRONMENT ASSESSMENT (PARENT REPORT):

The Family Eating and Activity Habits Questionnaire (see Appendix 30) is a 32-item parent-report assessment to assess the health behaviours of family members as well as the nature of the home environment [121]. It has high internal consistency (0.76-0.87) and test-retest reliability (0.75-0.89). These data will provide context for the children's behavioural outcomes, and allow us to examine the impact of the coaching on the family over time, which will also be examined in qualitative interviews with parents and children.

Post-Study

Following completion of the study, both child and their parent will be thanked and provided with a \$20 gift card for each visit (\$25 for the final visit) as a token of appreciation. Participants will also be offered volunteer hours. Families will be reimbursed for their parking expenses. Additionally, all participants who have completed all of the assessments will be entered into a prize draw for a gift card of \$150 at the end of the study. Participants and their parents will be asked if they wish to receive a summary of the research once the study is completed.

DATA ANALYSES

Sample characteristics will be summarized using descriptive statistics. Inferential statistics are not used in feasibility studies [82].

PRIMARY OBJECTIVE: Feasibility will be assessed using descriptive statistics using our *a priori success criteria* [82]. We will explore any sample/group differences between completers (complete Time 1 and Time 4 measures) and non-completers. We will also determine if there are sample and

Children and Teens in Charge of their Health: A feasibility study of solution-focused coaching to foster healthy lifestyles in children and young people with physical disabilities.

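### The Stratification feasibility criterion scores chance baseline balance instead of whether the stratified allocation was carried out correctly

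*Combined protocol and SAP*

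**What the plan says.** In the combined protocol and SAP, Study Assessments (primary objective) introduces the feasibility table with "Trial feasibility will be assessed using the following pre-identified criteria". Its Stratification row has two entries: "Intervention/control groups similar for age and gender" and "Intervention/control groups comparable on diagnosis and functional mobility". Neither carries a numeric limit, although the recruitment, attrition and adherence rows and the fidelity score do. Data Analyses treats the table as success criteria fixed in advance for the primary objective, to be judged descriptively, and states that inferential statistics are not used.

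The Randomization section says: "Group allocation occurs after baseline assessment, stratified by diagnosis and recruitment site". It implies blocks of undisclosed size: "Randomization block size will not be known to research staff to ensure blinding". Recruitment states "We will recruit 15 children with SB and 15 children with CP", and Design states "One group (n=15) will work with a coach trained in SFC-Peds eight times over six months", with a control group of the same size.

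Functional mobility (Participant characteristics) is measured with one six-minute test for children who walk and a different one for those who do not. No rule is given for putting the two on a common scale.

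**The concern.** The row and the allocation scheme do not match. Of the four variables in the row, only diagnosis is a stratification factor. The other stratification factor, site, is missing from the row.

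Baseline measures are completed before allocation. If the randomisation is sound, an arm difference in age, gender or mobility can only be the luck of one draw of 30 children. It carries no information on whether a larger trial can recruit, retain or allocate participants. For diagnosis the opposite holds: a scheme that runs as planned passes almost automatically.

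Meanwhile, what can go wrong in practice has no success criterion. This includes a child entered in the wrong stratum or an allocation taken out of sequence. Challenges includes a check of assessor blinding, but that is a different matter. At stake is whether one listed criterion of the primary objective can mean anything when it is reported.

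**Working it through.** The row has no figure of its own to reproduce. The check is how often a correctly randomised trial of this size would look imbalanced.

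**Inputs from the documents.** 15 per arm (Design); 15 children with SB and 15 with CP (Recruitment); stratification by diagnosis and site, in blocks (Randomization).

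**Assumptions, because the documents give none.** Imbalance means a standardised mean difference (SMD) above 0.5 for age or mobility, or a gender gap of at least 20 percentage points. The three covariates are independent. Mobility is treated as one continuous score. Block size is 2, 4 or 6.

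**Step 1: age and mobility, each.** The standard error of the SMD is √(2/15) = 0.365. P(|SMD| > 0.5) = 2 × [1 − Φ(0.5/0.365)] = 0.171. Simulation with the estimated SD (200,000 runs) gives 0.182.

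**Step 2: gender.** With 15 of 30 children boys, the number of boys in one arm is hypergeometric (30, 15, 15). A gap of at least 20 points means 6 or fewer, or 9 or more, boys in that arm: probability 0.466. With 12 or 18 boys of 30, the probability is 0.264. Treating each arm instead as an independent binomial (15, 0.5) gives 0.362.

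**Step 3: at least one of the three.** The formula is 1 − (1 − p)² × (1 − g), where p comes from step 1 and g from step 2.

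- 15 of 30 boys: 1 − 0.818² × 0.534 = 0.64
- 12 or 18 of 30 boys: 1 − 0.818² × 0.736 = 0.51 (0.49 with p = 0.171)
- Binomial gender model, p = 0.171: 1 − 0.829² × 0.638 = 0.56
- Age and mobility only: 1 − 0.818² = 0.33

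A stricter SMD limit of 0.25 has p = 0.500. The first figure then rises to 1 − 0.500² × 0.534 = 0.87.

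**Step 4: diagnosis.** Permuted blocks were simulated in four diagnosis-by-site strata (10,000 runs per scenario, three assumed site splits).

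| Allocation | Diagnosis gap ≥ 20 points | Gap ≥ 30 points |
|---|---|---|
| Stratified, block 2 | 0% (largest gap 6.7 points) | 0% |
| Stratified, block 4 or 6 | 0% to 2.3% (largest gap 20 points) | 0% |
| Not stratified | 47% | 14% |

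A small gap can remain, because 15 per diagnosis is an odd number and blocks may be incomplete.

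**The case against.** The strongest reply is that the cut-offs above are not the protocol's. The row is worded loosely, feasibility is judged descriptively, and the table is not uniformly pass/fail: one fidelity entry merely asks how remote coaching went. This stands as a limit on the percentages. It does not rescue the row. Without a threshold, the verdict on a criterion fixed in advance is decided after the data are seen, and no choice of threshold turns chance into evidence of feasibility.

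The diagnosis check is also not wholly empty. If correct execution nearly forces balance, a gross imbalance would point to an allocation error. That is true, but a direct audit finds such errors with more certainty, and it also finds those that leave the totals balanced. Mobility may be partly balanced through its link with diagnosis; the documents give no correlation, so this cannot be quantified.

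Two stronger readings are tempting and are not supported:

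- A reader might infer that missing this row would make the trial not feasible. No section contains such a progression rule, and Challenges provides for adaptation through the ADePT process.
- A reader might infer that the observed imbalance will determine the stratification factors of the full RCT. No section says so. Standard care links future stratification to differences in standard care between groups and sites. Data Analyses looks at differences by site, disability and mobility to guide the target sample.

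Nor does it follow that the RCT factors should be picked by their correlation with outcomes in this pilot. The 95% interval around r = 0 is about ±tanh(1.96/√27) = ±0.36 with 30 children. It is ±tanh(1.96/√12) = ±0.51 with the 15 coached children who alone have COPM and GAS scores.

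**Conclusion.** The concern holds for this one criterion. As written, the row is nearly certain to pass on diagnosis, is left to chance on age, gender and mobility, ignores site, and has no threshold. The mismatch with the Randomization section follows from the text alone.

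The size is illustrative: a sound trial of 15 v 15 would miss on at least one of age, gender and mobility roughly 50% to 64% of the time. That rests on the assumed limits (SMD above 0.5, gender gap of at least 20 points), on independent covariates, and on between 12 and 18 boys among the 30. The harm is a misleading result on one listed criterion of the primary objective. It is not an automatic failure of the feasibility study, and no allocation or outcome analysis is affected.

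**What to change.** Replace the Stratification row with a criterion on execution:

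- every child is allocated in sequence and in the correct diagnosis-by-site stratum;
- there are no allocation errors;
- the arm difference within each stratum is at most half the block size, the most that permuted blocks allow.

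Whoever holds the schedule should make this check, because the block size is hidden from research staff. Report age, gender, diagnosis, site and functional mobility by arm descriptively, with no pass or fail, and give the walk and push tests separately.

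The cost is one reworded table row and a brief allocation audit. No further data are needed from families.

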DEMOGRAPHICS: Gender, date of birth, ethnicity, diagnoses, medications, current sports involvement (see Appendix 19 for demographics form). Questions from the International Study of Childhood Obesity, Lifestyle and the Environment survey (see Appendix 20) about the child's environment (e.g. accessibility of play areas) will also be collected [107].

FUNCTIONAL MOBILITY: The six-minute walk test for walkers [108] and the six-minute push test for non-walkers [109] (see Appendix 21).

Primary outcome measure

ISSUE IDENTIFICATION AND GOAL ATTAINMENT (CHILD REPORT):

Within-group change will be assessed using the Canadian Occupational Performance Measure (COPM) (see Appendix 22), which identifies the person-centred goal performance issues to improve, and assesses changes in occupational performance and satisfaction. Participant goal attainment will be assessed using Goal Attainment Scaling (GAS) (see Appendix 23), by defining five levels of goal attainment, thus ensuring that all attainment levels are mutually exclusive and measurable. This is an

Children and Teens in Charge of their Health: A feasibility study of solution-focused coaching to foster healthy lifestyles in children and young people with physical disabilities.

objective measure of behaviour change [110]. To minimize bias, GAS and COPM re-assessment will be conducted by a coach who has not worked with the child.

Secondary outcomes measures:

Between group change will be examined using the following measures:

BEHAVIOURAL ASSESSMENTS (CHILD REPORT):

Physical activity: The Habitual Activity Estimation Scale [111] (see Appendix 24) estimates time spent inactive, somewhat inactive, somewhat active, and very active, and shows good correlation with moderate to vigorous PA measured by accelerometry in our population ($p=0.02$) [112, 113].

Diet: The Dietary Screener Questionnaire (see Appendix 25) assesses dietary intake over the past 30 days and is validated against 24 hour multiple recall [114].

PSYCHOSOCIAL ASSESSMENTS (CHILD REPORT):

Self-determination: The *Arc's Self-Determination Scale* (see Appendix 26) has excellent reliability/validity with children with disabilities [64] and will assess self-determination to provide insight into potential mechanisms of behaviour change.

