Self-efficacy: The *PA Self-efficacy Scale* (see Appendix 27) assesses confidence in the ability to be physically active when faced with challenges [115], with good internal consistency ($\alpha=.54-.71$) and test-retest reliability (ICC= .61-.82). High self-efficacy scores are significantly associated with greater moderate-vigorous physical activity [116]. *Self-efficacy for healthy eating* (see Appendix 28) assesses participants' feelings of competence for making healthy food choices in: social, emotional, and typical situations [117]. Higher scores are associated with healthy food intake ($\beta = .33, p < .01$), test-retest reliability (ICC= .80) [118].

BODY COMPOSITION (CHILD ASSESSMENT):

Children and Teens in Charge of their Health: A feasibility study of solution-focused coaching to foster healthy lifestyles in children and young people with physical disabilities.

Weight, height/length, waist circumference, and skinfold thickness (see Appendix 29 for record form) will be assessed, using standard guidelines [119].

Weight: Participants will be weighed minimally clothed (e.g. t-shirt, light shorts) without shoes to the nearest 100 grams using a chair scale.

Height: Those able to stand will be measured to the closest millimeter with a portable stadiometer or length measuring board. For those with severe contractures, careful segmental measurement will be conducted of the child's length in supine. Arm span and ulna length will also be measured as they offer useful proxies for length in children with lower extremity deformities [127, 128].

Body Mass Index (BMI): BMI will be calculated using both height and length as kilograms per meter squared (kg/m^2) and classified using Centres for Disease Control and Prevention cut-offs (85th–95th centile=overweight, above 95th percentile=obese) [120].

Waist circumference: Waist circumference (WC) has been shown to correlate well with fat mass as measured by dual-energy X-ray absorptiometry (DXA) [129-132] and has been specifically recommended for assessing body fat of children with SB [133] WC will be measured using a flexible tape measure at the narrowest level between the lower costal border and the iliac crest, over light clothing. Children with WC \geq 90th percentile have shown to be at higher risk of cardiovascular indicators [134, 135]. The RA will confirm lesion level using medical records and note any bulky masses, liposuction incision marks or spinal curvature.

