SECONDARY OBJECTIVE: Measure responsiveness will be established by pre-post intervention differences using effect sizes (Cohen's *d*) and confidence intervals both within and between groups. It is well accepted to examine mean score changes for clinically significant differences pre and post intervention without calculating statistical significance (e.g. a score change of at least 2 points on the COPM is considered clinically significant [38]). We will therefore be able to assess the potential value of SFC-Peds over receiving printed materials only by examining goal scores over time. Our secondary outcomes will be compared with objective behaviour change (goal attainment) for concordance (e.g. whether successful goal attainment corresponds with increased self-determination). We will examine differences in outcome measures by disability, functional mobility, gender and age.

CHALLENGES

Our intervention (SFC-Peds) is largely virtual to reduce burden and enhance adherence [43]. All participants will receive gift cards for completing assessments to reduce attrition; this is a key feasibility outcome, especially in the control group. To reduce possible biases, participants will not meet during the study and coaches will not be involved in standard care. Standardized training (by 3 certified coaches) will be provided. Assessors will be asked which group they think participants are in; blinding success is indicated by accuracies at or below chance level. If adaptations are needed for the RCT, 'A process for Decision making after Pilot and feasibility Trials' (ADePT) [124] will be followed.

KNOWLEDGE TRANSLATION (KT)

A KT planning template [40] will ensure our findings have maximum reach yet are appropriate for feasibility study outcomes. The plan capitalizes on close collaboration of knowledge users and researchers within our investigative team. Integrated KT is promoted throughout the project by the involvement of clinical, family and knowledge user stakeholders, to ensure that the outputs meet the needs of the end users [125]. Holland Bloorview Research Family Engagement Committee members

Children and Teens in Charge of their Health: A feasibility study of solution-focused coaching to foster healthy lifestyles in children and young people with physical disabilities.

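### A within-group effect size on raw BMI, waist or skinfolds in 10–18 year-olds includes growth, and the responsiveness analysis does not exempt these measures from it

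*Combined protocol and SAP*

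**What the plan says.** The inclusion criteria admit children "Between the age of 10 – 18 years inclusive". Body composition is assessed in both arms at baseline and at about 6, 9 and 12 months (Assessment Timings; Study Assessments, secondary objective).

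On the scale of measurement, the Body Composition section states that "BMI will be calculated using both height and length as kilograms per meter squared" and that the result is "classified using Centres for Disease Control and Prevention cut-offs". For waist, "WC will be measured using a flexible tape measure at the narrowest level". Triceps and subscapular skinfolds are taken as thicknesses, and body fat is derived from them by equation. No z-score, and no other continuous score standardised for age and sex, is named for any of these.

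Three statements bear on the contrast:

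- Data Analyses, secondary objective: "Measure responsiveness will be established by pre-post intervention differences using effect sizes", namely Cohen's d, with "confidence intervals both within and between groups". No measure is excepted.
- Secondary outcomes measures, the heading above body composition: "Between group change will be examined using the following measures".
- Design: "The control group will allow us to control for information, maturation, repeated testing and attrition over the 12 month study".

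The same Data Analyses paragraph compares secondary outcomes with goal attainment. Goal attainment is measured in the coached arm only.

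**The concern.** Children of this age change in weight, height, waist and fat distribution over 6 to 12 months whether or not they are coached. A pre-post effect size inside the coached arm cannot separate that change from a response to coaching. The control arm can, and the protocol gives maturation as one reason for having it, but a within-group d makes no use of it.

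The CDC classes do not solve the problem. A child can move well within a class without leaving it, and a class membership is not a quantity from which Cohen's d is computed.

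The comparison with goal attainment has a related weakness, because there is no control arm for it. Growth common to all coached children shifts the direction of change, so it affects any reading of whether goal attainment goes with improvement. Growth that differs by age and sex adds variation unrelated to coaching and blurs a correlation.

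What is at stake is the secondary objective: a body measure could look more or less responsive than it is.

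**Working it through.** **Plan figures.** The plan gives no effect size, SD or growth rate for body composition, so there is no figure of its own to reproduce on this point. Its one power statement (n=15, effect size 0.55, p<0.10, power 0.80) concerns Goal Attainment Scaling and is unaffected by growth.

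**Inputs for BMI (all assumed).** Growth of 0.4–0.8 kg/m² in 12 months; SD of individual change 1.0–1.5; baseline SD 4–6. Both SDs are shown because the protocol does not say which one standardises Cohen's d.

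**Growth-only within-group d = mean growth ÷ SD, with no coaching effect:**

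| Interval | Change SD | Baseline SD |
|---|---|---|
| 12 months | 0.4/1.5 = 0.27 to 0.8/1.0 = 0.80 | 0.4/6 = 0.07 to 0.8/4 = 0.20 |
| 6 months (half the growth, same SDs) | 0.2/1.5 = 0.13 to 0.4/1.0 = 0.40 | 0.2/6 = 0.03 to 0.4/4 = 0.10 |

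The upper end on the change SD pairs the largest growth with the smallest SD. If the change SD is smaller over six months than over twelve, the six-month figure falls by less than half.

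**Second set of assumptions, not tied to BMI units.** Let growth be g = 0.05–0.30 baseline SD per year and the pre-post correlation r = 0.80–0.95. Write m = g × months/12. Then d is m on the baseline SD and m/√(2(1−r)) on the change SD.

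- 12 months: 0.05–0.30 (baseline SD); 0.08–0.95 (change SD). The top value is 0.30/√(2×0.05) = 0.95.
- 6 months: 0.03–0.15 (baseline SD); 0.04–0.47 (change SD).

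**Between groups.** If mean growth is the same in both arms, the expected contribution is m − m = 0.

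**Simulation.** There were 15 children per arm, equal mean growth in both arms, no coaching effect, g = 0.10–0.20, r = 0.90–0.95 and 40,000 repeats per setting. The within-group 95% interval lay wholly above zero in 6–21% of trials at six months and 13–63% at twelve, against 2.5% without growth. The between-group interval excluded zero in about 5%, as it should. The simulation does not model a chance difference in age between arms.

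**Apparent precision.** On the change SD, the approximate standard error of d is 1/√15 = 0.26 within a group and √(2/15) = 0.37 between groups. The figure that contains growth would therefore also look the more precise.

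**The case against.** The strongest reply is that the protocol already assigns contrasts by measure. The goal measures (COPM and GAS), which exist only in the coached arm, are introduced for within-group change. Body composition comes under the between-group heading. On that reading, the reference in Data Analyses to both contrasts covers the two sets together, and nobody intends a within-group d on BMI. This largely stands as a reading of intent. However, the Data Analyses sentence governs how responsiveness is established and does not repeat the assignment, so the two sections need to be brought into line. The reply also leaves the comparison with goal attainment untouched.

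Other points stand:

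- The size rests entirely on assumed inputs. On the baseline SD it is small, and a pre-post contrast over a six-month intervention halves the assumed growth. No size has been worked out for waist or skinfolds.
- The CDC class is not the only age reference. The protocol cites a 90th-percentile waist threshold and excludes children below the fifth percentile, and outcomes are to be examined by age and gender. None of these gives a standardised change score.
- This is a secondary objective in a 30-child feasibility study that declares no inferential statistics.

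A reader might infer that the plan would count growth as a response to coaching. The documents do not support that. If growth raises BMI, it runs against the hoped-for benefit, and it would pass for response only if any non-zero d were read that way. The direction for skinfolds cannot be fixed from the documents. Nor does the plan say that outcomes for the full trial will be chosen on a within-group d.

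**Conclusion.** The point holds in a limited form. As written, the responsiveness analysis permits a within-group d on unstandardised body measures in growing children, and such a figure includes growth. For BMI, growth alone would give about 0.27–0.80 on the change SD or 0.07–0.20 on the baseline SD at 12 months, and roughly half that at six months, if the assumed growth and SDs are right. The planned between-group d has an expected growth contribution of about zero, so the design already contains the main safeguard.

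One qualification applies to that safeguard. Randomisation is stratified by diagnosis and site, not by age or sex. With 15 per arm, a chance difference in age or puberty could leave some growth in a single between-group estimate. Balance on age and gender is checked only as a feasibility criterion.

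No stated figure in the plan is shown to be wrong, and the primary feasibility and acceptability objective is unaffected. The change is worth making because it is cheap and serves the stated secondary objective.

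**What to change.** 1. In Data Analyses, secondary objective, state that the responsiveness of BMI, waist and skinfolds (with derived body fat) is judged on the baseline-adjusted between-group difference, reported as an effect size with its confidence interval. This brings the section into line with the heading under Secondary outcomes measures.
2. Convert BMI to age- and sex-specific z-scores from the CDC reference already named. Use the z-score for effect sizes and for the comparison with goal attainment, and keep kg/m² and the classes for description.
3. Because BMI may be computed from height or from length, use the same measure for a given child at every visit.
4. Label any within-group d on waist or skinfolds as including growth, and say which SD standardises every d.

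The cost is a few sentences and a conversion from date of birth and gender, both already collected; no new assessment is needed. The drawback is that the reference curves, and proxy measures of length, may fit children with spina bifida or cerebral palsy imperfectly. A z-score may then not remove all the growth, so the between-group contrast should remain the main safeguard.
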